10.7. Interim analysis

There will be not any interim analysis performed in this study.

10.8. Sample size

Sample size was calculated based on the primary outcome measures of C_{max} and AUC. Changes in the response values from the literature were taken from Grimaldi et. al.⁴⁵ for two outcomes, peak concentration (C_{max}) and bioavailability/area-under-the-curve (AUC), at two treatment doses. With respect to C_{max} , estimations from G*Power indicated a sample size of 6 would be sufficient to detect the established criterion difference (critical $t=2.57$).

The post-treatment mean difference in C_{max} from the literature was found to be 0.66 and was replicated during simulation with confidence intervals indicating a significant difference {0.36, 0.96}. Both the observed mean and median test statistics was found to be greater than the critical t (mean $t=4.23$, median $t=3.88$). Mean power was found to be slightly lower than expected (84% versus 86%) although median power was significantly larger (92%). Accordingly, six subjects would be sufficient to detect a difference in C_{max} between two doses of CAP. With the enrollment of 8 subjects, the study will be sufficiently powered even with a dropout rate of 25%.

Similar results were found for bioavailability, as measured as AUC, although at an attenuated effect, with an indicated increase in subject count to a minimum of 7 (critical $t=2.45$). Simulation verified a mean difference of 5.25 that would be expected to be significant based on the simulated confidence intervals {2.43, 8.09}. AUC was also found to be similarly powered, with a mean observed power of 83% and a median power of 93%. Accordingly, a sample size of seven is more than sufficient to meet the proposed criterion for CAP analyte bioavailability. With the enrolment of 8 subjects, the study will be sufficiently powered with 1 dropout (14%). Given the short duration of the study, we expect that a dropout rate of only 1 subject is reasonable. Eight total subjects were proposed for the dose comparison of Aim 1, which would allow for reductions in the detectable shifts of both peak concentration (37% of literature effect; $\Delta C_{max}=0.42$) and bioavailability (31% of literature effect; $\Delta AUC=3.63$) allowing for even greater powering to detect a dose effect of CAP.

Based on previously described bench results, gender is anticipated to potentially play a role in CAP metabolism, which may limit the ability to pool results. Maintaining the variances used in the calculations detailed above, the study would still be powered to see the anticipated dose effects within either gender with reduced powers of 75% and 67% for C_{max} and AUC bioavailability respectively.

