4.3. Study Population

4.3.1. Number of participants

Eight mildly demented elderly volunteers on cholinesterase inhibitor therapy (n=4 each female and male) 65-85 years of age will be screened and enrolled in the study. We estimate that we will need to screen approximately twelve potential participants to meet the eight volunteers needed to complete the study. We anticipate a possible dropout rate of 1 participant (14%) However, we are still powered to see differences between doses with a 25% drop out rate resulting in 6 remaining subjects.

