9.3. Detection of *Centella asiatica* derived compounds in plasma and urine

Biological levels of *Centella asiatica* triterpenes, caffeoylquinic acids, and their metabolites will be assessed in both plasma and urine using high-performance liquid chromatography coupled to tandem mass spectrometry (HPLC-MS/MS). Plasma calibration curves will be made using pooled baseline human plasma from the study participants (one teaspoon (5 mL)/participant) separated by gender. The blank plasma will be spiked with increasing doses of commercially available reference triterpenes, caffeoylquinic acids and known metabolites, as well as appropriate internal standards (see below). If the blank plasma is found to contain traces of the analytes, we will calculate the true concentration by back extrapolation using the method of standard addition. A pooled baseline urine sample taken from participants (separated by gender) will be used as a "blank" urine sample for spiking with standards.

Triterpenes; Plasma (200 µl) and urine samples (3000 µl) will be mixed with phosphoric acid and internal standard (chrysin) before incubation with *E. coli* glucuronidase and *S. aerogene* sulfatase to release the analytes of interest from glucuronide and sulfate conjugates. Incubated samples are passed through a Supelco Supelclean™ C8 column, washed with dilute aqueous acetic acid to remove salts, and eluted with ammoniacal methanol. The eluant is vacuum dried, reconstituted in 200 µl of 1:1 methanol: ammonium acetate and filtered through a 0.2 µM spinfilter to remove residual particles before analysis. HPLC-MS/MS will be performed on an Applied Biosystems Q-Trap 4000 LC-MS instrument. The analytical method to be used is a modification of that described by Nair et al. (Nair, Menon et al. 2012) Chromatographic separation will be achieved using a Poroshell 120 EC18 column and methanol:ammonium acetate gradient. Triterpenes will be detected as their ammonium adducts with positive ion mode electrospray ionization using the following MS/MS transitions: AA (506/453) and MA (522/451), and chrysin will be detected as the molecular ion (255/255).

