10.4. Primary and secondary hypotheses

- The primary hypothesis is that the triterpene and caffeoylquinic acid components in CAP will be orally bioavailable, such that administration of CAP will result in elevations from baseline values of the plasma concentration of *Centella* triterpenes, caffeoylquinic acids (CQAs), and CQA metabolites, and that the magnitude of this elevation will be higher for the 4g dose of CAP than the 2g dose.
- A secondary hypothesis is that absorption of compounds from CAP will result in an increase in antioxidant potential of the plasma.
- An additional secondary hypothesis is that consumption of a single dose of CAP will be safe and well tolerated.
- An additional secondary hypothesis is that consumption of a single dose of CAP will result in activation of the NRF2 antioxidant pathway over a 6 hour period.

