10.6. Specimen analysis

Each CAP derived analyte will be identified by its retention time and characteristic mass spectral fragmentation pattern using selected reaction monitoring. The peak area ratio to the appropriate internal standard will be identified and evaluated against the standard calibration curve of each analyte. Each analyte's concentration will be used to generate a concentration-time curve for pharmacokinetic profiling. Pharmacokinetic (PK) profiling of the triterpenes, CQAs and their metabolites will use non-compartmental analysis (NCA) to calculate common PK parameters such as peak concentration (C_{max}), the time at peak concentration (t_{max}) and the total 10 hour bioavailability represented by the total area under the curve (AUC_{0-10}). These will be compared to the mouse data in order to assess appropriateness of dosing level. Other calculable NCA metrics will also be determined, such as the elimination half-life ($t_{1/2}$) calculated from the profile tails and the mean residency time (MRT) of the compounds in plasma. Descriptive assessment will be done at each of the doses to give basic PK summarization of the various CA compounds and total antioxidant compounds measured by FRAP. NRF2 antioxidant pathway related gene and/or protein levels will be compared in PBMCs from the screening visit, the baseline study visit sample and hourly up to 6h following CAP administration. Dose dependence of the study outcomes will be determined by evaluation of the within-subject differences in study outcomes between the 2g and 4g CAP doses.

Assumptions of normality will be confirmed using outcome density distributions alongside utility from formal tests, such as the Anderson-Shapiro. In instances of normality violation, statistical transformation such as natural logs and square roots will be considered as will non-parametric equivalent tests such as the paired Wilcoxon rank-sum test. Standard diagnostics will be very conservative given the limited number of available subjects but clearly obvious outliers will be removed as necessary. Non-continuous variables such as t_{max} will have frequency distributions compared between doses using chi-square testing. Although all CA compounds of interest and PK parameters are defined a priori, multiple comparison correction to p-values will be applied as necessary, with final two-tail significance defined at $p < 0.05$.

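### The power figures in 10.8 (and the dropout statement in 4.3.1) hold for one uncorrected Cmax or AUC contrast; they leave out the multiplicity correction that 10.6 foresees for a multi-analyte primary outcome

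*Combined protocol and SAP*

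**What the plan says.** **Sample size (10.8).** For Cmax, "a sample size of 6 would be sufficient to detect the established criterion difference", with critical t = 2.57; simulated mean power is 84%, expected power 86% and median power 92%. The conclusion for Cmax is "With the enrollment of 8 subjects, the study will be sufficiently powered even with a dropout rate of 25" percent. For AUC the minimum is 7 (critical t = 2.45), with mean power 83% and median 93%; "a sample size of seven is more than sufficient to meet the proposed criterion for CAP analyte bioavailability", and one dropout is allowed. Mean differences and intervals are given, but no SD of the within-subject difference.

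**Number of participants (4.3.1).** The dropout claim returns without the restriction to Cmax: "we are still powered to see differences between doses with a 25% drop out rate", leaving 6 subjects.

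**Primary hypothesis and outcome (10.4, 10.5).** The outcome is Cmax and AUC0-10 of plasma analytes, in the plural. The hypothesis covers triterpenes, caffeoylquinic acids (CQAs) and CQA metabolites, and states that "the magnitude of this elevation will be higher for the 4g dose of CAP than the 2g dose".

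**Analysis (10.6).** Two-sided significance is set at 0.05, and "multiple comparison correction to p-values will be applied as necessary". No family, number of tests or method is given.

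**The concern.** A power statement should describe the test that will be run. Here power is worked out for single contrasts at an unadjusted 5%, while the analysis section expects a correction over a primary outcome with several analytes and two parameters each. Once a correction is applied, the stated power no longer describes the analysis. How far it drops depends on the family and the method, and the plan leaves both open.

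Section 4.3.1 adds a second mismatch. It presents 6 completers as enough for the dose comparison in general, whereas 10.8 needs 7 for AUC, which is the other half of the primary outcome.

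At stake is whether the study, especially after one or two dropouts, can be called adequately powered for its primary outcome as analysed.

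**Working it through.** **1. Reproduce the stated critical values.** For a paired t-test with n − 1 degrees of freedom:
- t(0.975; 5 df) = 2.571, against 2.57 stated at n = 6.
- t(0.975; 6 df) = 2.447, against 2.45 stated at n = 7.

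Both match an unadjusted two-sided 5% test. Splitting 5% over two tests would need 3.16 and 2.97.

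**2. Back-solve the effect size.** No SD is given, so the standardised paired difference dz is solved from

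power = P(|T| > t_crit), T ~ non-central t(n − 1, dz·√n),

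taking the stated powers as design powers (an assumption; see the objection).

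| Outcome, n | Stated power | dz |
|---|---|---|
| Cmax, 6 | 84% (mean) | 1.516 |
| Cmax, 6 | 86% (expected) | 1.562 |
| Cmax, 6 | 92% (median) | 1.737 |
| AUC, 7 | 83% (mean) | 1.325 |
| AUC, 7 | 93% (median) | 1.570 |

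**3. The 4.3.1 claim, uncorrected.** AUC power at n = 6 is 74% with dz = 1.325 and 86% with dz = 1.570. The 25% dropout arithmetic itself is right (8 × 0.75 = 6), but 10.8 supports it for Cmax only.

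**4. Smallest correction: 5% split over Cmax and AUC of one analyte (alpha = 0.025 each).**

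| Outcome | n | Unadjusted (stated) | At 0.025 |
|---|---|---|---|
| Cmax | 6 | 84–92% | 70–82% |
| AUC | 7 | 83–93% | 70–84% |
| Cmax | 8 | – | 89–96% |
| AUC | 8 | – | 79–91% |

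**5. A multi-analyte family.** Section 9.3 gives detection transitions for 2 triterpenes (asiatic and madecassic acid) and 8 CQAs, CQA groups or metabolites: mono-CQAs, di-CQAs, caffeic, ferulic, isoferulic and dihydrocaffeic acid, 4-methylcatechol and 4-ethylcatechol. That is 10 analytes × 2 parameters = 20 contrasts. This is my count; the plan gives none.

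Benjamini-Hochberg at 5% was simulated over 10 Cmax and 10 AUC contrasts, all carrying the full effect, with dz from the mean to the median figures in step 2 and between-contrast correlation of 0, 0.5 or 0.8:
- Cmax, 6 completers: about 69–91%.
- AUC, 7 completers: about 77–93%.
- Both outcomes, 8 completers: 85–99%.

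The ends at 6 and 7 completers are good to about one percentage point, depending on which Cmax and AUC effect sizes are paired.

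**The case against.** **The cited sentence is already limited to Cmax.** In 10.8 it closes the Cmax paragraph, AUC has its own sentence, and the critical values are printed, so a careful reader can see the level used. This stands for 10.8. It does not cover 4.3.1, where the limit is dropped.

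**It is a pilot.** Much of the analysis is descriptive, section 1.1 ties dose identification to plasma levels seen in mice, and the correction is conditional. Sizing such a study per contrast is legitimate. This stands and lowers the weight. But the plan states a primary dose hypothesis, a 0.05 threshold and adequate power, and those should agree with each other.

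**The effect sizes are uncertain.** Mean and median powers from simulation may be observed powers rather than design powers. A mean of 83% and median of 93% at n = 7 also fit dz of about 1.45–1.50. True power would then be about 89–91%, and two-test AUC power about 78–81% at n = 7 and 86–89% at n = 8. This stands, and the low ends of the AUC ranges depend on the other reading.

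**Stronger readings that the documents do not support.**
- A reader might infer that the study is underpowered. Bonferroni over 20 contrasts at n = 8 would give Cmax 47–63% and AUC 34–51%, but the plan names neither that method nor that family. If all contrasts carry the full effect, Benjamini-Hochberg keeps 85–99% at full enrolment.
- A reader might infer that multiplicity was ignored. It was not: 10.6 foresees a correction but does not finish the rule.
- The within-gender "reduced powers of 75% and 67" percent in 10.8 might be taken as evidence of a larger effect. They conflict with the same section: dz of 1.52–1.74 gives Cmax power of 54–65% at n = 4, not 75%. They are not used here.

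**Conclusion.** The point holds in a limited form. The power figures in 10.8 are per contrast at an unadjusted two-sided 5%, which the critical values confirm exactly. They leave out the correction that 10.6 foresees for a primary outcome with several analytes. Section 4.3.1 extends the 6-completer claim beyond Cmax, although 10.8 needs 7 for AUC.

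The loss is modest if all 8 complete and material mainly with dropout or a stricter method. Its size is indicative only: it assumes that the stated powers are design powers, a count of 20 contrasts that is mine, and, for Benjamini-Hochberg, that every contrast carries the full effect. The mismatch between sections needs none of these assumptions.

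The weight is low, and the point does not put the conduct of the study in doubt.

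**What to change.** 1. **10.8:** label the power figures as per contrast at unadjusted two-sided 5%, and restate power at the level actually used for 6, 7 and 8 completers. Give the SD assumed for the within-subject difference, and reconcile the within-gender powers with the main calculation.
2. **4.3.1:** limit the 25% dropout statement to Cmax, or align it with the 7 completers needed for AUC.
3. **10.6:** replace the open-ended correction with a fixed family and method. For example: Benjamini-Hochberg at 5% over the 4g minus 2g differences in Cmax and AUC0-10 of the sponsor's a priori analyte list, with the quantifiable analytes fixed before unblinding and other PK parameters reported as estimates with 95% confidence intervals.
4. **Analyte list:** the sponsor should confirm it. Section 9.3 gives no detection transitions for the triterpene glycosides (named in 10.3) or for dihydroferulic and dihydroisoferulic acids (listed in Table 2 of 3.1), so taking the family from 9.3 as it stands could narrow the endpoint unnoticed.

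**Cost:** text only, with no added participants or samples. The stated power becomes somewhat less favourable. Benjamini-Hochberg limits the expected share of false findings, not the chance of any; if the latter is wanted, Holm would serve but costs more power.

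### The within-gender powers (75% and 67%) and the n=8 detectable shifts in section 10.8 fit a one-sided test, although the plan tests two-sided

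*Combined protocol and SAP*

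**What the plan says.** All references are to the combined protocol and SAP.

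- **Test.** Section 10.6 bases dose dependence on within-subject differences between 2 g and 4 g, "with final two-tail significance defined at" p < 0.05.
- **Planning step.** Section 10.8 needs six subjects for Cmax (critical t 2.57) and seven for AUC (critical t 2.45). The Cmax difference "from the literature was found to be 0.66 and was replicated during simulation"; the AUC difference is 5.25. Cmax power at n=6 is 86% expected, 84% simulated mean and 92% simulated median. AUC power at n=7 is 83% mean and 93% median.
- **Shifts at n=8.** The section adds that eight subjects lower what can be detected, "which would allow for reductions in the detectable shifts of both peak concentration (37% of literature effect" with 0.42 beside it, and 31% with 3.63 for AUC.
- **Within gender.** The closing paragraph of 10.8 keeps the same variances and says the dose effect could still be seen in either gender, "with reduced powers of 75% and 67% for" Cmax and AUC. Section 4.3.1 enrols four women and four men, so n=4.

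Section 10.8 gives no SD, and states neither sidedness nor target power for the n=8 shifts or the within-gender powers.

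**The concern.** The sample-size step is two-sided, but the sensitivity figures that follow look one-sided. If so, the stated power and detectable differences are more favourable than the analysis in section 10.6 can deliver.

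The within-gender figures matter most. Section 10.8 expects that gender may limit pooling and offers 75% and 67% as reassurance. Section 5.6 plans gender contrasts as input to powering later work. A reader relying on these figures could take a null result within one gender as informative when the chance of detecting the full literature effect was near one half.

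A smaller matter is that the percentages printed beside 0.42 and 3.63 do not say clearly whether they are the shift or the reduction.

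**Working it through.** **Method.** Paired t-test power from the noncentral t distribution: df = n−1, noncentrality = √n × difference/SD, and critical value t(0.975, df) two-sided or t(0.95, df) one-sided.

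**1. Sidedness of the planning step.** t(0.975, 5) = 2.571 and t(0.975, 6) = 2.447 reproduce the stated 2.57 and 2.45. One-sided values would be 2.015 and 1.943. The planning step is therefore paired and two-sided at 0.05.

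**2. SD of the within-subject difference (back-solved; an assumption).**
- Cmax, n=6, difference 0.66: 84% power needs difference/SD = 1.516, so SD = 0.66/1.516 = 0.435. 86% needs 1.562, so SD = 0.4225.
- AUC, n=7, difference 5.25: 83% power needs 1.325, so SD = 5.25/1.325 = 3.96.
- AUC from the stated interval {2.43, 8.09}, dividing by 1.96: half-width 2.83, SE 2.83/1.96 = 1.444, SD = 1.444 × √7 = 3.82.

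**3. The later figures, both ways.** Ranges run over SD 0.4225–0.435 (Cmax) and 3.82–3.96 (AUC).

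| Figure in section 10.8 | One-sided power | Two-sided power |
|---|---|---|
| Within gender, Cmax, n=4 (stated 75%) | 74–76% | 54–56% |
| Within gender, AUC, n=4 (stated 67%) | 65–67% | 44–47% |
| Cmax shift 0.42, n=8 | 79–81% | 65–68% |
| AUC shift 3.63, n=8 | 75–78% | 61–64% |

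The within-gender powers are reproduced one-sided and missed by about 20 percentage points two-sided.

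**4. Detectable shift at n=8 with 80% power (the 80% is an assumption).** The required difference/SD is 1.156 two-sided and 0.978 one-sided.
- Cmax two-sided: 1.156 × 0.4225 = 0.49 to 1.156 × 0.435 = 0.50, which is 74–76% of 0.66. One-sided: 0.41–0.43, which contains the stated 0.42.
- AUC two-sided: 1.156 × 3.82 = 4.4 to 1.156 × 3.96 = 4.6, which is 84–87% of 5.25. One-sided: 3.74–3.88. The stated 3.63 lies a little below this and far below the two-sided range.

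**5. Most favourable stated inputs.**
- Cmax: the 92% median power gives SD 0.380. The interval half-width gives 0.30/1.96 × √6 = 0.375. Two-sided power for 0.42 is then 77–78%, and the 80% shift is 0.43–0.44.
- AUC: the 93% median power gives SD 3.34. Two-sided power for 3.63 is then 75%, and the 80% shift is about 3.9.
- Within gender, two-sided power rises to 65–66% (Cmax) and 57% (AUC). One-sided it would be 83–84% and 77%, so these smaller SDs do not reproduce the stated 75% and 67%.

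**6. Percentages.** 0.42/0.66 = 63.6%, a reduction of 36.4%. 3.63/5.25 = 69.1%, a reduction of 30.9%. Read literally as shares of the effect, 37% and 31% would be shifts of 0.37 × 0.66 = 0.24 and 0.31 × 5.25 = 1.63, which are not the shifts printed.

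**The case against.** **The SD and the target are not in the plan.** This stands. No single SD reproduces every stated t, power and interval, so exact replacement values cannot be fixed from the documents. Under the most favourable inputs the Cmax shortfall against 80% is small. Still, two-sided power stays below 80% for both shifts at every SD consistent with the stated mean or median powers. The shifts pass only if the printed intervals are t-based (SD about 0.286 and 3.06), giving 94% and 82%. That reading implies 99% power at n=6 and 96% at n=7, against the stated 84–86% and 83%.

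**The shifts are a supplementary remark.** This also stands. The sample size rests on the full literature effect. Two-sided power for that effect at n=8 is about 96–99% (Cmax) and 89–97% (AUC). A reader might infer that eight subjects are too few for the pooled comparison; these figures do not support that.

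**The percentages.** A reader might infer that 37% and 31% are miscalculated, or that a third of the literature effect is detectable. The sentence speaks of reductions and prints the absolute shifts, so the percentages are most naturally the sizes of the reductions. The fault is in the wording.

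**The intervals.** A reader might also infer that {0.36, 0.96} and {2.43, 8.09} wrongly use 1.96 in place of t. Their widths fit 1.96, but section 10.8 presents them as simulation results without giving their construction. Percentile limits of simulated means would look nearly the same ({0.36, 0.96} at SD 0.375; {2.44, 8.03} at SD 3.82). With the same SEs, t multipliers give about {0.27, 1.05} and {1.72, 8.78}, which still exclude zero. No error is established there.

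**Conclusion.** The point holds for the sidedness of the later figures. The within-gender powers are overstated by about 20 percentage points for the planned two-sided test, and the n=8 shifts are smaller than that test can detect with 80% power. The within-gender finding is the firmer of the two, because both stated powers are reproduced one-sided at SDs implied by the plan's own figures. For the shifts, the one-sided match is close for Cmax and approximate for AUC.

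The conclusion rests on a paired t-test, SDs back-solved from the stated figures, the same variance in each gender, and all participants completing. The 80% target used to judge the shifts is an assumption. The consequence is limited to the stated sensitivity and within-gender claims.

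**What to change.** In section 10.8:

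1. State the SD of the within-subject difference for Cmax and AUC, its source, the sidedness and the target power, and recompute from these.
2. Until then, restate the within-gender powers as about 55% (Cmax) and 45% (AUC) two-sided. Remove the statement that the study remains powered within either gender and describe those comparisons as exploratory, in line with section 5.6.
3. Restate the n=8 detectable shifts at two-sided 0.05 and 80% power: about 0.49–0.50 for Cmax (0.43 at the most favourable SD) and about 4.4–4.6 for AUC (3.9 at the most favourable SD).
4. If 0.42 and 3.63 are kept, give their two-sided power and describe them as reductions of about 36% and 31%, that is, shifts of 64% and 69% of the literature effect.

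The cost is a recalculation, some rewording and less favourable stated figures. The sample size and conduct of the study do not change.

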 - Safety and tolerability of single doses of CAP determined by participant interviews, biometrics, electrocardiography, laboratory assessment of liver and kidney function, vital signs and questionnaires
 - The level of triterpenes, caffeoylquinic acids, and their metabolites in a pooled urine sample collected over 10 h after CAP administration.
 - Activation of the NRF2 antioxidant response element pathway in peripheral blood mononuclear cells (PBMC) over 6 hours following CAP administration.

Intervention and duration

This is a study using a product composed of a water extract of the botanical *Centella asiatica*. The C_{max} , T_{max} and other pharmacokinetic parameters and tolerability assessments of two doses of CAP (2g and 4g) will be compared to one another. Participants will be in the study for up to two months. The minimum time a participant could be on study would be six weeks.

Sample size and population

The target population is elders aged 65-85 years old with a diagnosis of mild cognitive impairment for which they are currently on cholinesterase inhibitor therapy. There will be 4 male and 4 female participants in the study. This is a randomized crossover study, so no stratification will be implemented in randomization.

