5.6. Randomization, blinding and stratification

Randomization: Randomization will use an arm equivalence design to promote equal numbers of participants for each order schema. Randomization will occur within 72 hours of completion of the screening and baseline assessments collected at the screening visit and 72 hours prior to study intervention initiation. The order in which the doses are administered will be randomized so that some data will be available for both doses in case of dropouts after the first visit.

Blinding: All participants will be blinded to the dose they will be receiving at each visit. We have developed a formulation that tastes and looks very similar at each dose. The investigator administering the intervention and the analyst performing the LC-MS analysis of collected plasma will be blinded as to the dose of the product administered. The LC-MS analyst will also be blinded as to the time point of collection. The principal investigator, [name], is authorized to break the blind.

Stratification: Participants will be stratified by gender so that each dose level (2g or 4g) is administered to equal numbers (n=8) of each gender. Although exploratory in nature, contrasts between gender and cognitive impairment status will be calculated for powering and pilot data purposes.

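### The within-gender power claimed in Section 10.8 (75% and 67% on 4 people) does not hold at the plan's two-tailed 0.05, and the plan never says that the pooled dose comparison decides

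*Combined protocol and SAP*

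**What the plan says.** The synopsis fixes the gender split: "There will be 4 male and 4 female participants in the study". Section 10.8 sizes the trial for the paired 4 g versus 2 g comparison. It needs 6 people for Cmax and 7 for AUC, and adds that "Eight total subjects were proposed for the dose comparison of Aim 1". The section closes by warning that "gender is anticipated to potentially play a role in CAP metabolism, which may limit the ability to pool results". It then reassures that "the study would still be powered to see the anticipated dose effects within either gender", with power of 75% for Cmax and 67% for AUC.

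The analysis text is in Section 10.6: "Dose dependence of the study outcomes will be determined by evaluation of the within-subject differences" between the two doses. It mentions no gender term and no split. It sets two-tailed significance at 0.05, names a paired Wilcoxon test as the fallback if normality fails, and says that "multiple comparison correction to p-values will be applied as necessary", without naming a method or a family of tests.

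Section 5.6 adds: "Although exploratory in nature, contrasts between gender and cognitive impairment status will be calculated for powering and pilot data purposes".

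**The concern.** Two things are at issue.

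The first is the power claim. A group of 4 leaves 3 degrees of freedom, and powers of 75% and 67% look high beside the 84-86% that the plan reports for 6 people and the 83% for 7. A reader who trusts those figures would believe that a gender-specific dose test is a sound substitute for the pooled one.

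The second is the missing rule. Section 10.8 raises the possibility of not pooling and describes the gender-specific comparison as powered, but no section gives a test, threshold or timing for that choice. The exploratory label in Section 5.6 attaches to contrasts between genders. It does not clearly cover the dose test within each gender, and it does not say which dose test decides. A choice made after seeing the gender pattern could select whichever contrast looks significant, and it would give up most of the advantage of having 8 paired differences.

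**Working it through.** **Inputs.** From Section 10.8: Cmax, n=6, critical t 2.57, power 84% simulated and 86% expected, mean difference 0.66 with interval 0.36 to 0.96. AUC, n=7, critical t 2.45, mean power 83%, mean difference 5.25 with interval 2.43 to 8.09. From Section 10.6: two-tailed 0.05. From the synopsis: 4 men and 4 women. The standard deviations are not printed, so the standardised paired effect d (mean difference divided by the SD of the differences) has to be back-solved.

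**Confirming the test.** The two-sided 0.05 critical values are 2.571 on 5 df and 2.447 on 6 df. The plan's main calculation is therefore a two-sided paired t test.

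**Effect sizes.** Power = P(T > t_crit), where T is non-central t with n−1 df and non-centrality d√n.
- Cmax: 84% at n=6 gives d=1.52, and 86% gives d=1.56.
- AUC: 83% at n=7 gives d=1.33. Reading the interval half-width, (8.09−2.43)/2 = 2.83, as 1.96 standard errors gives SD = 2.83/1.96×√7 = 3.82 and d = 5.25/3.82 = 1.37.

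**Power at n=4 and n=8.** For n=4 the non-centrality is 2d, on 3 df. The critical t is 3.182 two-sided and 2.353 one-sided.

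| Parameter | d | n=4, two-sided | n=4, one-sided | Stated | n=8 pooled, two-sided |
|---|---|---|---|---|---|
| Cmax | 1.52-1.56 | 54-56% | 74-76% | 75% | 95-96% |
| AUC | 1.33-1.37 | 45-47% | 65-67% | 67% | 89-91% |

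The stated within-gender figures reproduce one-sided and not two-sided.

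**Cross-check in the other direction.** To have 75% two-sided power at n=4, d would have to be 1.99, which implies 97% power at n=6. To have 67%, d would have to be 1.79, which implies 97% at n=7. The plan reports 84-86% and 83%.

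**Sensitivity to the source of d.** The plan's median powers (92% at n=6, 93% at n=7) give two-sided n=4 power of 65% and 57%. Reading the Cmax interval as ±1.96 standard errors gives 66%. Reading the intervals as t intervals gives 85% (Cmax) and 64% (AUC), but those effects imply 99% power at n=6 and 96% at n=7, which contradicts the mean powers in the same section.

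**Rank fallback.** Taking the paired Wilcoxon test as the signed-rank test, the smallest two-sided p with 4 people is 2/2⁴ = 0.125.

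**False-positive rate under possible rules.** The plan states no rule, so every rule below is an assumption. The rates come from 2,000,000 simulated null trials with normal paired differences, 4 men and 4 women, two-sided 0.05, one analyte and one parameter.

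| Rule | Rate |
|---|---|
| Pooled test only | 5.0% |
| Split if gender-by-dose p<0.05; either gender counts | 7.6% |
| Same, split at p<0.10 | 8.7% |
| Same, split at p<0.20 | 9.8% |
| Always split; either gender counts | 9.8% |
| Any of pooled, men or women counts | 12.4% |
| Split at p<0.05; both genders must succeed | 4.9% |
| Split at p<0.05; Bonferroni across genders | 6.4% |

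As a check, two independent tests at 0.05 give 1−0.95² = 9.75%, which agrees with the always-split row.

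**The case against.** The strongest reply is that the remark in Section 10.8 is a comment on power and not an analysis rule. Section 10.6 bases dose dependence on within-subject differences with no gender term, Section 10.8 assigns all eight people to the dose comparison, and Section 5.6 calls gender contrasts exploratory. That stands. A reader might infer that Section 10.8 authorises the primary comparison to switch from 8 people to men and women separately. The documents do not say so; they leave the question open.

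A reader might also infer that the trial's false-positive rate is 7.6-12.4%. The documents do not support that as a property of the plan. The range needs a split chosen from the data and unadjusted credit for success in either gender. Stricter rules give 4.9% or 6.4%, and Section 10.6 promises some correction, though an unspecified one. Under the rank fallback neither gender of 4 could reach significance, so a split would then cost power without adding false positives.

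Finally, a reader might argue that the gender remark is mistaken because gender effects cancel in within-subject differences. That holds on a log scale or for additive effects, but Section 10.6 only considers logs if normality fails. On the untransformed scale, with linear kinetics, AUC = F×dose/CL, so the 4 g minus 2 g difference is F×2 g/CL. Doubling clearance in one gender halves its difference. The remark about metabolism is therefore coherent. It still does not make pooling invalid, because the pooled mean over 4 men and 4 women is then the average dose effect.

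This is also a phase 1 pilot, in which dose appropriateness is judged against mouse data, so the stakes are modest. None of these replies rescues the 75% and 67%.

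**Conclusion.** The within-gender power claim is wrong as written. At the plan's two-tailed 0.05, power on 4 people is about 54-56% for Cmax and 45-47% for AUC, against the stated 75% and 67%. This rests on a paired t test with normal differences and on effect sizes recovered from the plan's mean powers, with the AUC interval giving the upper AUC value. The exact SDs are not given. More favourable readings of d raise the two-sided figures, but a reading that reached the stated values would contradict the powers at n=6 and n=7.

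The missing statement that the pooled contrast decides is a real but smaller gap. Its possible cost is an error rate per analyte and parameter of up to about 7.6-12.4% under a data-driven, unadjusted rule. That is conditional on a rule the plan does not contain. Correcting this is advisable; it does not undermine the pooled design, which is well powered on the plan's own assumptions.

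**What to change.** In Sections 10.6 and 10.8, state that the pooled within-subject 4 g versus 2 g contrast of Cmax and AUC0-10 is the deciding analysis whatever the gender results. State that dose differences within each gender, and the gender-by-dose difference, are exploratory and are reported as estimates with 95% confidence intervals.

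Delete the claim that the study is powered within either gender, or replace its figures with the two-sided ones (about 54-56% and 45-47%, to be recalculated by the sponsor from the actual SDs). The remark that gender may affect metabolism can stay, with a note that the pooled mean then estimates the average dose effect.

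The cost is a few sentences. The plan gives up any confirmatory claim within a gender.
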